9.2.4 Randomized Treatment Adverse Events

A summary table using the FAS Safety Analysis Set including the number of patients with at least one event, and the total number of events will be presented for the AE variables below.

- TEAE^{1, 3}
- Serious TEAE^{1, 3}
- Grade 3/4/5 TEAE²
- Drug-related TEAE¹
- Serious drug-related TEAE¹
- Drug-related grade 3/4/5 TEAE²
- TEAE leading to reduction of ¹⁷⁷Lu-PSMA-617 dose¹ or of BSC/BSoc¹
- TEAE leading to interruption of ¹⁷⁷Lu-PSMA-617 treatment¹ or of BSC/BSoc¹
- TEAE leading to permanent discontinuation of ¹⁷⁷Lu-PSMA-617 treatment¹ or of BSC/BSoc¹
- Fatal TEAE²

¹AE variables to be tabulated by SOC and PT by grade (including a total across all grades and all grades 3/4/5).

²AE variables to be tabulated by SOC and PT.

³TEAEs are to be tabulated by SOC and PT, including a total across all grades and all grades 3/4/5), and by ¹⁷⁷Lu-PSMA-167 cycle of onset.

A summary of serious and non-serious adverse events with number of occurrences will be produced (an occurrence is defined as >1 day between start and prior end date of record of same preferred term).

A listing for each patient will include the same variables as mentioned above in Section 9.2.3 except will include action taken regarding ¹⁷⁷Lu-PSMA-617 and action taken regarding Best supportive/Best standard of care. Non-treatment-emergent adverse events will be flagged.

To help evaluate the impact of the COVID-19 virus on the safety, the incidence of COVID-19 related adverse event preferred terms will be presented incorporating (a) COVID-19 related adverse events with an onset date prior to the start of the outbreak (i.e. pre-2020) and (b) all COVID-19 related adverse events occurring before the data cut-off. All COVID-related AEs will be included in the listings.

9.2.4.1 Sub-study

Similar analyses as described in Section 9.2.4 (excluding TEAEs by ¹⁷⁷Lu-PSMA-167 cycle of onset due to the small number of patients) will be performed using the Sub-study Safety Analysis Set. All AEs will be listed including COVID-related AEs.

9.2.5 Deaths

Summaries of all deaths, including deaths within 6 weeks and 3 months (12 weeks) of randomization (using the FAS and FAS Safety Set), on-treatment deaths or within 30 days of randomized treatment discontinuation (using the FAS Safety Set), and ⁶⁸Ga-PSMA-11 on-treatment deaths (using the PSMA-11 Safety Analysis Set) will be provided including the primary cause of death (including deaths due to COVID-19). All deaths will be listed and will include the details for 'other cause'.

9.2.5.1 Sub-study

A summary of all deaths and on-treatment deaths will be provided using the Sub-study Safety Analysis Set. A summary of ⁶⁸Ga-PSMA-11 on-treatment deaths will be provided using the PSMA-11 Sub-study Analysis Set. All deaths in the sub-study will be listed.

9.2.6 Long-term Follow up Adverse Events

During LTFU, new and existing AEs will continue to be followed, capturing only AE term and grade.

A summary table including the number of patients with at least one event, and the total number of events will be presented for the AE variables captured on the Long Term Follow-Up – Adverse Events CRF page below using the FAS Safety Analysis Set.

- AE¹
- Grade 3/4/5 AE²
- Fatal AE²

¹AE variables to be tabulated by SOC and PT by grade including a total across all grades and all grades 3/4/5.

²AE variables to be tabulated by SOC and PT.

A listing will include the participant identifier, age, race, verbatim, preferred term, and toxicity grade.

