All AEs will be graded according to CTCAE v5.0. All AE monitoring and SAE recording and reporting will begin at the time of consent and will continue up to and including 30 days after the last dose of ¹⁷⁷Lu-PSMA-617 or the date of best supportive/best standard of care end of treatment decision, whichever is later. In addition, SAE recording and reporting will be continued in the long-term follow-up period. During long-term follow-up, SAEs are to be reported only if the investigator suspects a causal relationship to the study treatment.

SAEs experienced after the 30-day period following the last administration of randomized treatment, including during long-term follow-up, should be reported to Novartis Safety if the investigator suspects a causal relationship to the study treatment.

During long-term follow-up, for all renal toxicities, secondary malignancies and all SAEs, sufficient information will be obtained to permit an adequate determination of the outcome of the event and an assessment of the causal relationship between the AE and ¹⁷⁷Lu-PSMA-617, and/or best supportive/best standard of care. SAEs, renal toxicities and secondary malignancies felt to be associated with ¹⁷⁷Lu-PSMA-617, and/or best supportive/best standard of care will be followed until the event or its sequelae or the abnormal test finding resolves or stabilizes at a level acceptable to the investigator.

The investigator will promptly review AEs and abnormal test findings to determine if: 1) the abnormal test finding should be classified as an AE; 2) there is a reasonable possibility that the AE was caused by, ¹⁷⁷Lu-PSMA-617, and/or best supportive/best standard of care; and 3) the AE meets the criteria for a serious adverse event (SAE). If the final determination of causality is “unknown and of questionable relationship to the study drug” the adverse event will be classified as associated with the use of the study drug for reporting purposes. If the final determination of causality is “unknown but not related to the study drug” the determination and rationale will be documented in the patient’s case history. Renal toxicities and secondary malignancies will be recorded as AEs. Any AE determined to meet the criteria for a serious adverse event and considered related to the study drug (even a questionable relationship) should be recorded as an AE and reported as an SAE.

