8.1 Revision to the protocol and statistical analyses of rPFS and OS

The trial was originally designed to randomize 750 patients, targeting the primary analysis of rPFS with 457 events with a 1-sided alpha level of 0.001, an interim analysis of OS with a 1-sided alpha level of 0.001, to be conducted contemporaneously with the primary analysis of rPFS, and a final primary analysis of OS with 489 deaths with a 1-sided alpha of 0.023.

However, shortly after commencement of the trial, a high early dropout rate amongst those randomized to BS/BSC-only arm became evident with the majority of these dropouts withdrawing consent to follow-up. This meant that rPFS data could not be collected for these patients which consequently could result in bias in the analysis of rPFS. Remedial measures to curtail this phenomenon were implemented and made effective on March 5th, 2019. As part of the plan to address the early withdrawal of consent in the BS/BSC-only arm, the primary analysis of rPFS was altered to focus on patients prospectively randomized on or after March 5th, 2019; therefore, rPFS will be analyzed in these patients once 364 events have accrued with a 1-sided alpha level of 0.004. At time of this rPFS primary analysis, there will be an interim analysis of OS with a 1-sided alpha level of 0.001; this OS analysis will be on an ITT basis and will include all randomized patients (i.e., including those randomized before March 5th, 2019). Following the analysis of rPFS and the interim analysis of OS, a final ITT primary analysis of OS will be performed when 508 deaths have accrued with a 1-sided alpha level of 0.020. To achieve these analyses, the total number of subjects randomized into the trial was increased from N=750 to N=814. The revisions described do not alter the hypothesized treatment effects for rPFS and OS upon which the study was originally powered.

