5.3.2 Safety Populations

- **PSMA-11 Safety Analysis Set:** All patients who received a dose of ⁶⁸Ga-PSMA-11. This includes screened patients that are not enrolled (i.e., not randomized). Patients enrolled will be included in the treatment arm to which they were randomized.

- **FAS Safety Analysis Set:** The subset of patients in the FAS who received at least one dose of randomized treatment. Patients will be included in the treatment arm corresponding to the actual treatment received.

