9.2.2 General Convention

Any treatment-emergent event as defined in Section 9.2.1 missing the assessment of relatedness will be considered study drug-related.

In case a patient experienced the same event more than once, the maximum toxicity grade will be presented.

In all AE tables except the ones presented by Cycles, multiple occurrences of the same adverse events occurring in one individual are counted only once.

In all AE tables presented by cycle of onset, multiple occurrences of the same adverse events occurring in one individual within one cycle are counted only once.

AE summaries for ^{68}Ga -PSMA-11 and Randomized Treatment will include AEs occurring during the treatment-emergent period whereas AE summaries for Long-term Follow up will include new and existing AEs during the long-term follow-up period captured on the Long-Term Follow up CRF page. All AEs will be listed along with the information collected on those AEs. AEs will be summarized by number and percentage of patients having at least one AE, having at least one AE in each primary SOC and for each PT using MedDRA coding. The total number of events will also be provided. A patient with multiple occurrences of an AE will be counted only once in the respective AE category. A patient with multiple CTCAE toxicity grades for the same preferred term will be summarized under the maximum CTCAE toxicity grade recorded for the event. AE with missing CTCAE toxicity grade will be included in the total across all grades of the summary table.

In all AE summaries, the primary SOC will be presented alphabetically and the PTs will be sorted within primary SOC in descending frequency. The sort order for the PT will be based on their frequency in the ^{177}Lu -PSMA-617+BSC/BSoc arm for randomized treatment and long-term follow-up AE summaries and the frequency in the overall column for ^{68}Ga -PSMA-11 AE summaries.

9.2.3 ⁶⁸Ga-PSMA-11 Adverse Events

A summary table using the PSMA-11 Safety Analysis Set including the number of patients with at least one event, and the total number of events will be presented for the following variables:

- TEAE¹
- serious TEAE¹
- grade 3/4/5 TEAE²
- drug-related TEAE¹
- serious drug-related TEAE¹
- drug-related grade 3/4/5 TEAE²
- fatal TEAE²

¹AE variables to be tabulated by SOC and PT by grade including a total across all grades and all grades 3/4/5.

²AE variables to be tabulated by SOC and PT.

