A summary of serious and non-serious adverse events with number of occurrences will be produced (an occurrence is defined as >1 day between start and prior end date of record of same preferred term).

A listing will include the participant identifier, age, race, verbatim, preferred term, duration of the event, toxicity grade, seriousness, action taken regarding ⁶⁸Ga-PSMA-11, outcome, relationship to study drug, and start and end date. Non-treatment-emergent adverse events will be flagged.

9.2.3.1 *Sub-study*

Similar analyses as described in Section 9.2.3 will be done using the PSMA-11 Sub-study Analysis Set.

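### The long-term follow-up AE table describes any AE recorded in follow-up; it does not estimate the incidence of new late toxicity

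*SAP*

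**What the plan says.** - **Capture.** SAP 9.2.6: "During LTFU, new and existing AEs will continue to be followed, capturing only AE term and grade".
- **Content.** SAP 9.2.2: "AE summaries for Long-term Follow up will include new and existing AEs during the long-term follow-up period". The same section makes number and percentage of patients the convention for AE tables, with the total number of events. SAP section 9 shows results by arm.
- **Analysis set.** SAP 9.2.6 summarises the variables on the LTFU AE "CRF page below using the FAS Safety Analysis Set". SAP 5.3.2 defines that set as "The subset of patients in the FAS who received at least one dose of randomized treatment". Entry into LTFU is not a condition.
- **Listing.** SAP 9.2.6: "A listing will include the participant identifier, age, race, verbatim, preferred term, and toxicity grade". By contrast, the listing in SAP 9.2.3, whose variables SAP 9.2.4 largely reuses for randomized treatment, includes "action taken regarding ⁶⁸Ga-PSMA-11, outcome, relationship to study drug, and start and end date".
- **Who is followed.** LTFU depends on consent (SAP 3.1) and may be for survival only (Protocol 4.3). Protocol 8.1 reports high early dropout in the control arm, which "became evident with the majority of these dropouts withdrawing consent to follow-up".
- **Later protocol text.** For the period after the final OS analysis, Protocol 7.2 requires that "for all renal toxicities, secondary malignancies and all SAEs, sufficient information will be obtained to permit an adequate determination of the outcome", together with a causality assessment. The SAP is written on protocol version 4.0 and does not use this.

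**The concern.** A late-safety table is normally read as answering how often new toxicity appears after treatment and whether that differs by arm. Three features stand in the way. A toxicity that began on treatment and persists is counted again in LTFU. A treated patient who died on treatment, withdrew consent or chose survival-only follow-up stays in the all-treated group, although no LTFU AE could be recorded for him. And with no onset date and no person-time, a longer-followed arm has more opportunity to report events.

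No other planned AE analysis fills the gap. The treatment-emergent period in SAP 9.2.1 ends no later than 30 days after the last administration, and the safety topics of interest in SAP 9.2.7 are restricted to the on-treatment period. Late safety matters here: protocol versions 5.0 and 6.0 extended LTFU, and 6.0 did so to collect long-term safety data under a postmarketing requirement.

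**Working it through.** The documents state no LTFU AE rate, LTFU entry rate or LTFU duration, so there is no planned figure to reproduce. The check compares the text with what an incidence estimate needs, then gives illustrations.

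**1. Text**

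| Needed for incidence of new late events | What the plan provides |
|---|---|
| New events separated from ongoing ones | Pooled (SAP 9.2.2, 9.2.6) |
| Onset date | Not in LTFU capture or listing (SAP 9.2.6), although SAP 5.2 calls AE start and end dates required fields |
| Patients under observation | All treated patients (SAP 5.3.2) |
| Time under observation | Not used, although SAP 5 describes a last-contact date collected in LTFU |

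SAP 9.2.2 counts a patient once per AE category, which protects the patient counts. It does not say whether an ongoing AE recorded at successive contacts adds to the event total.

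**2. Unequal survival alone**

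Inputs: median OS of 13.7 months (active, alternative hypothesis) and 10 months (SAP 3.4). Assumptions: exponential survival, the same constant hazard *h* of a new late event in both arms, time counted from randomization, and follow-up ended only by death or the time horizon *T*.

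Death hazard: λ = ln 2 / median, so 0.0506 per month (active) and 0.0693 (control).
Crude proportion with an event: h/(h+λ) × [1 − exp(−(h+λ)T)].

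For h = 0.005 per month and T = 12:
- active: 0.005/0.0556 × (1 − exp(−0.667)) = 4.4%
- control: 0.005/0.0743 × (1 − exp(−0.892)) = 4.0%

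| h per month | T (months) | Active | Control | Crude ratio |
|---|---|---|---|---|
| 0.005 | 12 | 4.4% | 4.0% | 1.10 |
| 0.005 | 24 | 6.6% | 5.6% | 1.18 |
| 0.010 | 12 | 8.5% | 7.7% | 1.10 |
| 0.010 | 24 | 12.6% | 10.7% | 1.18 |

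Per person-time the rate is the same in both arms (12h = 0.06 or 0.12 per patient-year), a ratio of 1.00.

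**3. Unequal entry into LTFU alone**

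Reported percentage = share entering × risk among entrants. Take 5% risk among entrants in both arms; the entry shares are assumptions.

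| Entry, active / control | Reported | Ratio |
|---|---|---|
| 80% / 80% | 4.0% vs 4.0% | 1.00 |
| 80% / 60% | 4.0% vs 3.0% | 1.33 |
| 80% / 40% | 4.0% vs 2.0% | 2.00 |
| 60% / 80% | 3.0% vs 4.0% | 0.75 |

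With LTFU entrants as denominator every row is 5% vs 5%. The last row shows that the sign depends on the entry shares.

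**4. Carry-over alone**

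Assume 80% entry and 5% new-event risk in both arms, with carried-over events in a share *c* of entrants. Reported percentage = 0.8 × [1 − (1 − c)(1 − 0.05)].
- c = 10% in both arms: 11.6% vs 11.6%, ratio 1.00.
- c = 20% active, 10% control: 19.2% vs 11.6%, ratio 1.66.

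New events alone are 0.8 × 5% = 4.0% of treated patients in both arms.

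**The case against.** Several points on the other side stand.

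- **The table is legitimate as description.** The percentage of treated patients with any AE recorded in LTFU is a well-defined quantity, and no hypothesis test of AEs is planned. The treatment-emergent tables are unaffected.
- **The denominator is partly inferred.** SAP 9.2.6 itself names only counts and an analysis set; percentages come from SAP 9.2.2. SAP 5 excludes patients with missing data from percentages by default, but no rule classes a patient who never entered LTFU as missing.
- **Some late safety is covered elsewhere.** SAP 9.3 plans separate LTFU laboratory shift tables, grade 3/4 frequencies and liver thresholds, and SAP 9.2.5 covers deaths by cause. These help with renal and marrow toxicity but cannot show secondary malignancy, and the laboratory tables use the same all-treated set. SAP 6.1 shows the number continuing in LTFU by arm, though it is not linked to the AE table.
- **Timing.** SAP version 3.0 (18 January 2021) predates protocol version 5.0 (26 April 2021), so it could not have used the newer renal and malignancy requirement. That explains the gap; it does not close it, because Protocol section 8 still plans final safety analyses at the end of extended follow-up.

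A reader might go further and infer that control-arm withdrawals must create a spurious excess on the investigational arm. The documents do not support that. Protocol 8.1 describes dropout among randomized controls and gives no rate. Controls who left before treatment fall outside the safety set. Remedial measures took effect on 5 March 2019, with about 557 of 814 patients (68%) expected to be randomized on or after that date.

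**Conclusion.** The concern holds in a limited form. As planned, the LTFU AE table cannot separate new late events from carried-over ones and does not adjust for who was followed or for how long, so it should not be read as an incidence of late toxicity. Between-arm percentages could be distorted if entry, follow-up time or carry-over differ. They are undistorted if all three are equal.

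The only illustration anchored in the plan's own figures is unequal survival: a crude ratio of about 1.10 at 12 months and 1.18 at 24 months with no true difference in hazard. It rests on the design medians, exponential survival, a constant equal hazard and time from randomization. The entry and carry-over examples use assumed inputs and show only that the effect can be larger and can run either way. To call the rates wrong, or the arms not comparable, would go beyond what the documents show.

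**What to change.** Keep the planned table and add to SAP 9.2.6:

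1. A table of newly arising or worsened LTFU AEs, identified by matching LTFU term and grade to the dated on-treatment AE record, with carried-over events shown separately.
2. The number of treated patients per arm with at least one LTFU AE contact (for the LTFU laboratory tables, at least one LTFU sample), with percentages on that number beside the all-treated percentages.
3. Events, or patients with a new event, per 100 patient-years from the end-of-treatment visit to the last LTFU contact, by arm. Protocol 6.5 narrows AE collection to renal toxicity and secondary malignancy after the final OS analysis, so the table should state which period it covers.

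Going forward only, record onset date and relationship for renal toxicity and secondary malignancy on the LTFU page. Retrospective questioning is not a substitute: at the final OS analysis 508 of 814 patients are planned to have died, so onset could be recovered only from survivors. Reconcile SAP 5.2 (AE dates required) with SAP 9.2.6 (term and grade only).

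The cost is a SAP amendment, the matching program, and two fields for two event types at contacts already made every 3 months. There are two drawbacks. LTFU entrants are a post-randomization subset, so percentages on them are descriptive only. Matching on term and grade will also misclassify some events, for example a resolved toxicity that recurs.

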9.2.6.1 Sub-study

A listing of all AEs captured during long-term follow up will be provided.

9.2.7 Safety Topics of Interest

A safety topic of interest is a grouping of adverse events that are of scientific and medical concern specific to ⁶⁸Ga-PSMA-11 and ¹⁷⁷Lu-PSMA-617. These groupings are defined on a program level using MedDRA terms, SMQs (standardized MedDRA queries), HLGs (high level group terms), HLT (high level terms) and PTs (preferred terms). Customized SMQs (Novartis MedDRA queries, NMQ) may also be used. A NMQ is a customized group of search terms which defines a medical concept for which there is no official SMQ available or the available SMQ does not completely fit the need. It may include a combination of single terms and/or an existing SMQ, narrow or broad. The groups are defined according to the MedDRA terms defined in the program Case Retrieval Strategy (CRS) document and will be summarized. The latest version of the CRS document available at the time of the analyses will be used. For each specified safety topic of interest, number and percentage of patients with at least one event of the safety topic of interest occurring during the on treatment period will be summarized.

Summaries of these Safety Topics of Interest during ⁶⁸Ga-PSMA-11 treatment period (using PSMA-11 Safety Analysis Set) and during randomized treatment period (using the FAS Safety Analysis Set) will be provided by treatment arm, (specifying grade, SAE, relationship, leading to treatment discontinuation (if applicable), leading to dose interruption (if applicable), hospitalization, death etc.).

A listing of all grouping levels down to the MedDRA preferred terms used to define each Safety Topic of Interest will be generated.

9.2.7.1 Sub-study

A listing of Safety Topics of Interest during ⁶⁸Ga-PSMA-11 treatment period (using PSMA-11 Sub-study Analysis Set) and during ¹⁷⁷Lu-PSMA-617 treatment period (using the Sub-study Safety Analysis Set) will be provided.

9.3 Clinical Laboratory Determination

Local labs will perform hematology, chemistry, serum testosterone, and urinalysis testing. The following laboratory parameters are to be summarized:

- Testosterone
- Chemistry

sodium	LDH	Bicarbonate ¹
potassium	blood urea	calcium
total and direct bilirubin	nitrogen ²	glucose
ALP	creatinine	total protein
AST	urate	albumin
ALT	phosphate	
	chloride	
- Urinalysis³

urine pH	glucose
protein content	ketones
specific gravity	
appearance and color	
- Hematology

complete blood count (white blood cell count and differential)
red blood cell count
hemoglobin
hematocrit
platelet count

1. total carbon dioxide or equivalent is acceptable

2. urea is acceptable

3. Urinalysis parameters are only collected at screening. Appearance and color, glucose, ketones and protein content are captured as free-text and will only be listed (not summarized).

Hematology, chemistry and serum testosterone laboratory values and the change from baseline during randomized treatment will be summarized for each parameter by visit. Shift tables of the worst post-baseline on-treatment laboratory toxicity based on CTCAE v5.0 grading relative to baseline will be presented as well as the frequency of grade 3/4 toxicities. For laboratory tests where CTCAE grades are not defined, shift tables using low/normal/high/(low and high) classification to compare baseline to worst post-baseline on-treatment value will be presented. Frequency statistics for qualitative laboratory parameters will also be presented by visit. The summaries will include all laboratory assessments collected no later than 30 days after the last administration of randomized treatment (i.e. on-treatment).

The mean (\pm standard error) values over time will be plotted for hemoglobin, hematocrit, platelets, WBC, absolute neutrophil count, AST, ALT, BUN, and creatinine by treatment arm.

An additional summary of hematology, chemistry and serum testosterone laboratory values at screening will be provided for the PSMA-11 Safety Analysis Set.

Listings of all laboratory data and listings of laboratory toxicities \geq Grade 3 will be provided. Values outside of the laboratory's reference range will be flagged. Values collected later than 30 days after the last randomized treatment date will also be flagged. If laboratory values are provided as '<X' (i.e. below limit of detection) or '>X', prior to conversion of laboratory values to SI unit, these numeric values are set to X. The patient listings will indicate the CTCAE grade.

During long-term follow up, hematology and chemistry are collected every 3 months. Shift tables of the worst post-baseline laboratory toxicity during LTFU based on CTCAE v5.0

grading relative to baseline will be presented as well as the frequency of grade 3/4 toxicities. For laboratory tests where CTCAE grades are not defined, shift tables using low/normal/high/(low and high) classification to compare baseline to worst post-baseline value during LTFUP will be presented. These will be displayed in similar tables separately for LTFU using the FAS Safety Analysis Set. Laboratory assessments collected during LTFU will be included in the listings.

Liver function parameters

Liver function parameters of interest are total bilirubin (TBL), ALT, AST and alkaline phosphatase (ALP). The number (%) of patients with worst post-baseline values will be summarized by treatment arm using the FAS Safety Analysis Set only. The following summaries will be produced during the randomized treatment and long-term follow up, separately:

- ALT > 3xULN
- ALT > 5xULN
- ALT > 8xULN
- ALT > 10xULN
- ALT > 20xULN
- AST > 3xULN
- AST > 5xULN
- AST > 8xULN
- AST > 10xULN
- AST > 20xULN
- ALT or AST > 3xULN
- ALT or AST > 5xULN
- ALT or AST > 8xULN
- ALT or AST > 10xULN
- ALT or AST > 20xULN
- TBL > 2xULN
- TBL > 3xULN
- Concurrent ALT > 3xULN & TBL > 2xULN
- Concurrent AST > 3xULN & TBL > 2xULN
- Concurrent ALT or AST > 3xULN & TBL > 2xULN
- Concurrent ALT or AST > 3xULN & TBL > 2xULN & ALP < 2xULN
- Concurrent ALT or AST > 3xULN & TBL > 2xULN & ALP ≥ 2xULN

For single parameters (e.g. AST>3xULN), the worst value post-baseline is considered. For the combination of various parameters, the lab values need to be from the same assessment (concurrent assessment). Concurrent measurements are those occurring on the same date. In addition, a listing of all TBL, ALT, AST and ALP values for subjects with a post-baseline TBL > 2xULN, ALT> 3xULN or AST > 3xULN will be provided using the FAS Safety Analysis Set. Values meeting the criteria during randomized treatment and LTFU will be listed.

